### 3. Evaluation of Therapy Processes that Mediate Treatment Outcomes

The first set of analyses will evaluate whether the CAPS score mediates treatment response using methods described by Angell and colleagues (Angell et al., 2007). Mediation by the CAPS will be tested by adding it to a model in which proportion substance use days is regressed on group assignment. If there is an effect of treatment that is suppressed by adding the CAPS score to the regression equation, then CAPS score is a mediator of the treatment effect (Baron & Kenny, 1986).

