#### The Importance of Referral to Available VA Treatment for Substance Abuse and PTSD

The "RT" (Referral to Treatment) in "SBIRT" takes advantage of the range of effective substance abuse and PTSD treatments available for OEF/OIF Veterans at VA, and can have a large impact by engaging Veterans in those available treatments. VA facilities typically offer a wide range of substance abuse treatments and there is evidence that at VA, as is true elsewhere, the extent of participation in substance abuse treatment is associated with achieving abstinence (Moos, Humphreys et al. 1999).

Engaging Veterans in substance abuse treatment may help PTSD too. In an intriguing pharmacological clinical trial targeting both alcohol abuse and PTSD, participants' alcohol use

improved before PTSD symptoms did (Back, Brady et al. 2006). SBIRT referrals to substance abuse treatment do not preclude concomitant PTSD treatment; surveys of VA clinicians in substance abuse treatment settings show that they usually screen for PTSD and may then refer Veterans who screen positive for PTSD to specialized PTSD treatment providers (Young, Rosen et al. 2005). The large sample in this study will allow for cross-lagged analyses to determine the relative time course of changes in substance abuse with changes in PTSD symptoms and treatment attendance.

It is likely that some Veterans who attend SBIRT will insist on PTSD treatment instead of substance abuse treatment, and, consistent with a Motivational Interviewing approach, Veterans who insist on PTSD treatment after weighing their options will be supported in their choice. Fortunately, treatment focused on PTSD can also ameliorate substance abuse (Brady, Sonne et al., 2005). In uncontrolled studies, substance-using Veterans who received PTSD treatment were more likely to be abstinent than those who did not (e.g. Ouimette, Moos et al. 2003) and PTSD improvement has been associated with reduced alcohol use in clinical trials settings too (Back, Brady et al. 2006). The current standard of care is that *integrated treatment* be offered to people with concomitant substance abuse and psychiatric disorders (Morrissey, Jackson et al. 2005) and both VA Connecticut and the Tennessee Valley Healthcare Systems have clinicians based at their PTSD clinics who are specially trained to offer such integrated treatments.

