#### Hypotheses for Clinical Trial Component:

1. Veterans with substance use disorders receiving SBIRT will attend more weeks of substance abuse and/or mental health treatment and will have fewer days of substance use in the twelve weeks after the Compensation examination than Veterans assigned to No-Additional-Treatment. Secondary outcomes will include: (i) weeks attending any mental health treatment; (ii) proportion days using any alcohol, proportion days drinking to intoxication and (iii) PTSD as measured by the CAPS.
2. Preliminary analyses will determine whether the effect of SBIRT on outcomes is moderated by beliefs about disability.

Together, the findings will determine the effects of substance use and other factors on outcome and treatment engagement among Veterans presenting for Compensation evaluations for PTSD, and will determine the efficacy of an intervention to foster treatment engagement and abstinence.

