Standard procedures will be employed to see that the delivery of the study therapy and the collection of study data are separated. The Evaluative Component and Clinical Trial Component will be carried out by a different staff member for each Veteran. After the data collector completes the assessments of the Veteran eligible for randomization, the data collector will enter the information for urn randomization into the computer program, but the study therapist will actually give the software command to conduct the urn randomization and generate group assignment. All outcome evaluations will be conducted by the data collector, and Veterans will be asked not to tell the data collector whether SBIRT was delivered. In summary, the clinical trial is not adversely impacted by the presence of a preceding Evaluative Component.

It also is unlikely that the Evaluative Component will not be interpretable because of the Clinical Trial Component. The 480 Veterans who are not randomized (because they do not have risky alcohol use and/or substance use) will be compared to the 80 substance users randomized to No-Additional-Treatment, using a prospective observational design to determine effects of substance use. Both groups will receive serial assessments that are not likely to impact outcomes.

2. Power Analysis for Analysis of the Effects of Substance Use on Outcomes: The effects of substance abuse on outcomes will be analyzed by random effects regression analyses. The treatment attendance outcome will yield a value for each week (attendance or not) and PTSD severity will be assessed at three time points (baseline, 4 and 12 weeks). In the primary analysis, these repeated-measures outcomes will be regressed on substance use, with covariates included that represent potentially confounding differences between Veterans with and without substance use disorders. The proposed sample of 560 participants receiving No-Additional-Treatment, of whom 80 are substance users, has power  $> .80$  to detect standardized mean differences in linear slopes as small as  $\delta = .25$ , allowing for potential downward bias in effects from nonrandom group assignment (Optimal Design software version 1.77), and partial  $\eta^2$  of  $< .1$ , correcting for non-sphericity (G\*Power 3.1.2, Buchner et al., 1992-2009).

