Veteran's symptoms have gotten better with treatment." A confirmatory factor analysis will be conducted of the Disability Beliefs Scale to determine if the anticipated three factor structure emerges, and continuous subscale scores for each factor will be considered separately in the data analyses.

Items for the Disability Beliefs Scale were drawn from existing measures that rate related constructs. The items concerning the relationship between treatment and receipt of disability payments were adapted from items used in a completed study of supportive employment at VA (Rosenheck and Mares 2007). Items were also drawn from the "Negative Expectations" subscale of the Disability Application Appraisal Inventory (not the same scale that rates reasons for seeking disability payments).

6. Substance Use Calendar and Ethyl Glucoronide (ETG): The timeline follow-back Substance Use Calendar assesses substance use on a daily basis. The use of a calendar format prompts participants to remember key dates. It allows for collection of data points for participants who miss evaluation sessions and thus prevents missing data and problems associated with overlap of data points. Timeline follow-backs have been sensitive to change in research settings (Weiss, Greenfield et al. 1998) and can be valid in patients with concomitant psychiatric illness (Petrakis, Poling et al. 2005).

Ethyl Glucoronide is produced and equilibrates throughout nail beds, thus allowing measurement by any nail sample of sufficient weight. Approximately 10mg of nail is required for analysis, which can be obtained from 10mm (a quarter's width) of nail from each of ten digits. Nail-clippers soaked for 10 minutes in 70% rubbing alcohol are used for the actual clipping. Nail levels of ETG have correlated with self-reported number of drinks among college-aged women at .51 and men at .64, with the lower correlation among women possibly reflecting greater use of nail care products (Jones, Jones, et al., 2011).

M. Jones, J. Jones, D. Lewis, C. Plate, M. Fendrich, L. Berger, & D. Fuhrmann. (2011, June). Correlation of the alcohol biomarker ethyl glucuronide in fingernails and hair to reported alcohol consumed. Poster session at the annual conference for the Research Society on Alcoholism, Atlanta, GA.

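### The CAPS mediation rule tests neither time order nor an indirect effect, so it can report a consequence of reduced substance use as a mediator (secondary analysis only)

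*Combined protocol and SAP*

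**What the plan says.** In the combined protocol and SAP, section K (Data Analysis for Clinical Trial Component), item 3, the test consists of "adding it to a model in which proportion substance use days is regressed on group assignment". The conclusion that the decision rule draws is "then CAPS score is a mediator of the treatment effect", and the condition that it sets for this is "If there is an effect of treatment that is suppressed by adding the CAPS score to the regression equation". Two method sources are cited. The text sets no threshold, test or confidence interval for *suppressed*. It does not say which CAPS is used, whether use days are counted before or after that CAPS, or whether baseline CAPS or earlier use is adjusted for.

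Other sections give the timing. The schedule of assessments in section G puts CAPS at baseline, week 4 and week 12. The first clinical-trial hypothesis concerns "fewer days of substance use in the twelve weeks after the Compensation examination". The Substance Use Calendar "assesses substance use on a daily basis", so use can be divided at any CAPS visit.

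On direction, the Background section on referral to VA treatment reports a trial in which alcohol use "improved before PTSD symptoms did". The same section also says that treating PTSD can reduce substance use.

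**The concern.** Baseline CAPS precedes randomization and cannot carry an SBIRT effect, so a usable CAPS value must come from week 4 or week 12. If the outcome covers the twelve weeks named in the hypothesis, the first lies inside that window and the second at its end. A fall in CAPS may then be the result of reduced use and not its cause.

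Adding a consequence of the outcome to the model also moves the SBIRT coefficient towards zero. The written rule reads that movement as mediation. At stake is the account of how SBIRT works: the report could say that SBIRT reduces use by relieving PTSD when the data arose the other way round. Because *suppressed* is undefined, how often this happens depends on a choice left until after the data are seen.

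**Working it through.** **1. The plan's own figure.** The power analysis for the Clinical Trial Component gives effect .50, power .80, alpha .05 and 128 analysable Veterans, with 20% loss allowed. A two-sided t-test with 64 per arm has noncentrality .5 x sqrt(64/2) = 2.83 and power .8015, and 128/0.80 = 160 randomized. The figure reproduces. It is used here only to set the scale.

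**2. Algebra with no mediation.** Let T be group, U use (SD 1 within arm), d = .50, and let CAPS depend only on U:

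- U = -dT + e
- CAPS = rU + sqrt(1 - r²) e'

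Within arm, CAPS has variance 1 and covariance r with U, so its coefficient in a model for U is r. The group difference in CAPS is -rd. The coefficient of T given CAPS is therefore -d - r(-rd) = -d(1 - r²). The SBIRT coefficient shrinks by r²: 9%, 16% and 25% at r = .3, .4 and .5. The true mediated effect is zero. The documents give no use-CAPS correlation, so r is an assumption.

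**3. How often the rule misfires.** This model was simulated with 64 per arm and 20,000 trials per value of r. About 80% of trials had a significant SBIRT effect on use. Among those, the share declaring CAPS a mediator was:

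| Reading of *suppressed* | r = 0 | r = .3 | r = .4 | r = .5 |
|---|---|---|---|---|
| Coefficient loses significance | 1% | 8% | 13% | 19% |
| Shrinks, with group-to-CAPS and CAPS-to-use both significant | 0.1% | 13% | 23% | 34% |
| Any shrinkage | 50% | 83% | 90% | 95% |

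Smaller runs move these ends by one or two points (for example 9-18%, 15-32%, 85-95%, and 48% at r = 0).

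**4. Sensitivity to the model.** A second model split use into weeks 0-4 and 5-12, with an assumed within-person correlation of .6, and let week-12 CAPS depend on the later use only. The total use over both periods was the outcome. With N = 128 and correlations .2, .3 and .5, the three readings gave 3%, 5% and 12%; 5%, 13% and 32%; and 72%, 83% and 94%. The size varies with the model, but the ordering of the readings is the same at r = .3 and above.

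**5. Does time ordering repair it?** In the second model, with the true CAPS-to-use path equal to zero, week-4 CAPS was tested as a predictor of use in weeks 5-12 (N = 128):

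| Analysis | .2 | .3 | .5 |
|---|---|---|---|
| Time ordering only | 26% | 52% | 93% |
| Time ordering plus adjustment for use in weeks 0-4 | 4.6% | 4.5% | 5.0% |

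Entries are the share of trials with a false significant path. At correlation .3, changing the within-person correlation to .3 or .8 gave 17% and 79% without the adjustment, and 5.2% and 5.3% with it. Both elements are needed.

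**The case against.** The strongest reply has four parts.

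- **The rule has a first condition.** It applies only if a treatment effect exists. A reader might infer from the 83-95% row that the plan would make a false mediation claim in most trials. The documents do not support that: *suppressed* need not mean any shrinkage, and half of trials shrink by chance when use and CAPS are unrelated. Under the stricter readings the rate is far lower.
- **The background supports both directions.** A reader might infer that the plan contradicts its own evidence by treating CAPS as mediator. It does not. The section that reports alcohol improving first also reports PTSD improvement associated with reduced alcohol use, and SBIRT supports Veterans who choose PTSD treatment. The mediation hypothesis is reasonable; the test cannot separate it from its reverse.
- **Temporal order appears elsewhere.** The Background mentions cross-lagged analyses, and section J, item 4 plans lagged effects of use on CAPS. This is partial mitigation at most. The section J models belong to Evaluative Aim 1, whose sample is the 560 Veterans who did not receive SBIRT, so they cannot show how SBIRT acts. Section K, item 3 invokes neither.
- **The cited method sources may add conditions.** They are not in the documents, so this can be neither credited nor excluded. The rule as written carries no such condition.

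**Conclusion.** The point stands for a secondary, mechanistic analysis. As written, the rule cannot distinguish SBIRT to PTSD to use from SBIRT to use to PTSD, and it leaves the deciding word undefined. If only use drives CAPS, a false mediator is declared, among trials with a significant SBIRT effect, in about 8-19% (loss of significance) or 13-34% (both paths also significant). The any-shrinkage figure of 83-95% must be read against 50% by chance. These figures rest on d = .50, 64 per arm, an assumed correlation of .3 to .5, a continuous normal outcome and a twelve-week outcome window, which section K, item 3 does not itself state.

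A reader might go further and doubt the trial's main result. Nothing here supports that: the primary outcomes, the intention-to-treat comparison and the sample size are untouched.

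**What to change.** Delete the attenuation rule and specify the following in section K, item 3:

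- **Mediator:** week-4 CAPS, adjusted for baseline CAPS.
- **Outcome:** use days after the week-4 visit up to week 12, adjusted for baseline use and for use up to that visit.
- **Estimate:** the indirect effect with a bootstrap confidence interval.
- **Reverse path:** use up to week 4 to week-12 CAPS, fitted in the randomized sample.
- **Wording:** a positive result is consistent with mediation, not proof of it, because CAPS is not randomized.

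This needs wording only, since the CAPS visits and daily calendar are already planned. Three downsides should be stated:

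- The outcome window falls from twelve weeks to about eight.
- SBIRT may take place up to two weeks after the examination, which can leave only about 4 - 2 = 2 weeks before week-4 CAPS. Benefit that comes later through PTSD treatment may be missed, and the plan keeps the week-12 visit partly to detect later effects.
- Use up to week 4 is measured after randomization and may itself be changed by SBIRT. Adjusting for it removes part of the early effect and limits the estimate to later effects.

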### 4. Evaluation of Factors Associated with Treatment Effects

To determine what factors are associated with response to any kind of counseling, potential predictor variables will be entered into the primary outcome analyses as covariates. Potential predictor variables include gender, type of trauma, use of an illicit drug, baseline PTSD severity as measured by the CAPS, depression as measured by the BDI, a history of TBI, and cognitive impairment as evidenced by a score below 26 on the MOCA. As noted in the data analysis plan for the evaluative component, other potential moderator variables will include attitudes concerning Compensation exams (Veterans' reasons for seeking Compensation on the Disability Appraisal Inventory, and beliefs about whether Compensation is influenced by treatment attendance, continuing symptoms, and substance use on the Disability Beliefs Scale).

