#### 5. Analyses of the Relationship Between Attitudes About Compensation examinations and Outcome

*(Evaluative Specific Aim 2: Attendance at treatment will be predicted by Veterans' perceptions that obtaining and maintaining VA benefits depends on attending PTSD treatment):*

We hypothesize and will test in HLM regression models whether attendance at substance abuse and/or mental health treatment (and other outcomes) are predicted by the following, after accounting for appropriate covariates:

a. Veterans' perception that obtaining and maintaining VA benefits depends on treatment. Veterans' perceptions concerning the linkage between their status and receiving benefits will be derived for the three scales of the Disability Beliefs Scale which reflect perceived linkage of benefits to: (i) engagement in VA mental health treatment, (ii) being symptomatic from PTSD, and (iii) being abstinent from drugs and/or alcohol. Other scales will be analyzed if the factor analysis of the Disability Beliefs scale reveals another factor structure.

b. Subscales indicating that (i) Validation, (ii) Self-Other Considerations and (iii) Financial concerns were Veterans' reasons for seeking Compensation, as rated on the Disability Application Appraisal Inventory (Sayer, Spoont et al. 2004). We hypothesize that Veterans who rate themselves higher in having applied seeking "Validation (of being ill)" will be more likely to attend treatment, and that Veterans with higher ratings in "Self-Other (e.g. someone else urges Veteran to seek award)" or who applied for financial gain would be less likely to attend treatment.

c. Interactions between Disability Application Appraisal and Disability Beliefs Scale subscale variables. Reasons for seeking benefits and beliefs about disability application appraisal may interact to make treatment attendance more or less likely.

Covariates in these analyses will include those reflecting three main domains that have been associated with treatment attendance (Koenen, Goodwin et al. 2003):

- Predisposing factors: demographic variables (age, gender)
- Enabling factors that facilitate access to treatment: study site, distance between home and medical center calculated using G.I.S. mapping
- Need for treatment: Substance Use, PTSD severity (CAPS total score) and depression severity (Beck Depression Inventory).

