#### 6. Analyses of the Relationship between Application Status (before Compensation examination vs. after, before receiving claim judgment vs. after) and Treatment Attendance (Evaluative Specific Aim3: Long-term attendance at treatment will be significantly impacted by the occurrence of the Compensation examination and determination of award):

Attendance at treatment will be regressed on time-varying covariates reflecting having had a Compensation examination, and having had a Compensation claim approved by the Veterans Benefits Administration. A secondary analysis will consider whether these time-varying covariates will significantly interact with attitudes concerning how disability is awarded.

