#### 2. Evaluation of Treatment Effects:

Evaluation of comparability of baseline characteristics of the two client groups will be conducted using chi-square tests for categorical variables and t-tests for continuous variables. If an unexpected difference is found and is related to the outcome, the potentially significant confounding variable will be added to the primary outcome analysis as a covariate.

The principal strategy for assessing the efficacy of the study treatments will be random effects regression, as described for the analysis of the effects of substance use on other outcomes. The focus of these analyses will be the ‘treatment group by time effects’ for each

hypothesis, and whether the slopes, or rates of change, of Veterans assigned to SBIRT differ from the slopes of those assigned to No-Additional-Treatment. The model will include appropriate covariates and the contrasts of SBIRT versus Control. The effects of site and the site-by-treatment interaction will be determined.

Our principal data analyses will be conducted on the intention-to-treat sample. We will attempt to follow all participants for assessments regardless of their retention in treatment. Intention-to-treat analyses will be supplemented by analyses to describe the consistency of findings across different definitions of the sample: e.g., treatment-exposed and treatment completers.

Secondary analyses will be conducted to account for the possibility that days without substance use data (scored as missing) are not randomly distributed. In these analyses, variables that distinguish people with missing substance use data from those with complete data will be included in the analyses as covariates or auxiliary variables (Graham, 2003).

A linear effect of time on outcome variables is being hypothesized but ancillary analyses will be conducted to determine if the effect of SBIRT treatment is better explained by a quadratic function, given the possibility of deceleration in rate of change.

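### Trial Hypothesis 2 asks whether disability beliefs moderate the SBIRT effect, but section K.4 states no treatment-by-belief term

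*Combined protocol and SAP*

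**What the plan says.** The second hypothesis for the Clinical Trial Component reads: "Preliminary analyses will determine whether the effect of SBIRT on outcomes is moderated by beliefs about disability".

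Section K.4 is the only place in the trial analysis plan that deals with these beliefs. Its stated purpose is this: "To determine what factors are associated with response to any kind of counseling". Its stated method is that "potential predictor variables will be entered into the primary outcome analyses as covariates". It lists seven candidate predictors (gender, trauma type, illicit drug use, baseline CAPS, BDI, TBI history, cognitive impairment). It then refers back to the evaluative plan and adds that "other potential moderator variables will include attitudes concerning Compensation exams", naming the Disability Application Appraisal Inventory reasons and the Disability Beliefs Scale. It gives no separate model for this second group.

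The primary trial model is in K.2: "The focus of these analyses will be the ‘treatment group by time effects’ for each" hypothesis. K.2 also says: "The effects of site and the site-by-treatment interaction will be determined".

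**The concern.** Moderation means that the size of the SBIRT effect depends on the level of belief. It is tested by an interaction between treatment and belief. A covariate coefficient answers a different question: whether belief is associated with the outcome when both arms are taken together. If an analyst follows K.4 literally, the output contains no estimate that bears on Hypothesis 2. A belief that is merely prognostic could also appear under a heading about treatment effects. The Background (Significance of Proposed Studies) treats these beliefs as modifiable and relevant to policy, so readers are likely to act on what is reported.

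**Working it through.** **1. What each model estimates.** Write the primary model as

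y = a + b1·T + b2·time + b3·(T × time),

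where T is the treatment arm and b3 is the SBIRT effect on the slope. Let B be a baseline belief score.

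- Covariate only: add b4·B. The SBIRT effect is still b3 at every value of B.
- Generous reading, with the covariate also predicting the slope: add b5·(B × time). The SBIRT effect is still b3 at every value of B.
- Moderation: add b6·(B × T) and b7·(B × T × time) as well. The SBIRT effect on the slope becomes b3 + b7·B. Hypothesis 2 is a statement about b7.

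**2. Whether b7 appears anywhere in the plan.**

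- K.2 names treatment-by-time and site-by-treatment. Neither involves belief.
- K.4 names covariates only.
- J.5, in the evaluative plan: "Interactions between Disability Application Appraisal and Disability Beliefs Scale subscale variables". These are scale by scale.
- J.6: a secondary analysis "will consider whether these time-varying covariates will significantly interact with attitudes concerning how disability is awarded". This is application status by attitude.
- J.1 defines the evaluative sample as the 560 participants who did not receive SBIRT. Nothing fitted there can estimate how the SBIRT effect varies.

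No treatment-by-belief term is stated.

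**3. The plan's own figure.** The Power Analysis for the Clinical Trial Component gives 128 participants for δ = 0.50, power .80, α = .05, with room for 20% loss. As a two-mean comparison (two-sided, 1:1, SD 1), n per arm = 2 × (1.960 + 0.842)² / 0.50² = 62.8, so 63 per arm or 126 in total. With the noncentral t, 64 per arm gives power .801, which matches 128. Then 128 / 0.80 = 160. Both figures reproduce. The plan states no power for moderation.

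**4. Precision of the interaction.** Section G.5 says that the Disability Beliefs subscale scores are continuous. With T coded ±½, B standardized and residual SD 1, SE(T × B) = 2/√N. The change in effect detectable with 80% power is (1.960 + 0.842) × 2/√N:

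- N = 128: 2.802 × 0.1768 = 0.50 SD per SD of belief.
- N = 160: 2.802 × 0.1581 = 0.44 SD per SD of belief.

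For a change of 0.25 SD per SD of belief, power is 29% at N = 128 and 35% at N = 160.

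**5. Covariate term against interaction term.** A simulation used N = 128, 4,000 runs, a 0.5 SD treatment effect, a standard normal belief score and one outcome per person. The percentages are runs with p < .05.

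| Truth | Covariate term | Interaction term |
|---|---|---|
| Moderation only (0.5 SD per SD of belief) | 5.2% | 78.6% |
| Prognosis only (0.5 SD per SD of belief) | 99.98% | 5.4% |

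The covariate term rejects at about the nominal error rate when there is moderation alone. It rejects almost always when there is none but the belief is prognostic.

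**6. Number of tests.** Three anticipated belief subscales and two primary outcomes give 3 × 2 = 6 interaction tests, with 6 × .05 = 0.3 false positives expected if no effects exist. Extending this to everything in K.4 (seven predictors plus six attitude and belief subscales) gives 13 × 2 = 26 tests and 26 × .05 = 1.3 expected.

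**The case against.** The strongest reply is that K.4 is incomplete rather than wrong. Grammatically, entry as covariates governs the list of predictors. The belief scales come in a later sentence under a different label, with no mode of entry given. The authors also know what moderation means: Evaluative Hypothesis 3 speaks of an effect being moderated, and J.6 tests it as an interaction. This stands in part. A reader might infer that the plan definitely commits to testing the wrong coefficient, and the text does not settle that. Still, the word joining the belief scales to the preceding list ties them to the only method given. Where the plan wants an interaction elsewhere, it names one. On the kindest reading the moderation model is unspecified, and the same repair is needed.

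Three other stronger readings are also unsupported:

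- **The trial cannot answer Hypothesis 2.** The Schedule of Assessments collects both belief measures at baseline, so no data are lost and added model terms can answer it.
- **The purpose stated in K.4 is empty because controls receive no counseling.** The control-condition section rules out only study-related therapy. Controls may attend usual VA or non-VA care, and attendance is a primary outcome.
- **Only a difference of about 1 SD between high- and low-belief groups is detectable.** That figure (0.99 SD at N = 128) assumes a 50/50 binary split. The subscales are to be analyzed as continuous scores.

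It is also fair that the hypothesis already calls these analyses preliminary, and that they are not among the primary measures in K.1.

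**Conclusion.** The point holds as a mismatch between a stated hypothesis and the only stated method. K.4 as written estimates prognosis, while Hypothesis 2 asks about differential effect. K.4 should be amended, but the matter is confined to a preliminary, non-primary analysis. The 128 and 160 do not depend on it, and neither does either primary comparison.

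The precision figures in steps 4 and 5 rest on assumptions that the documents do not give: a single-outcome approximation to the slope model, SD 1, two-sided α of .05 and 1:1 allocation. The slope-variance inputs behind the plan's power software are not stated, so the detectable change on the slope scale could differ. N = 160 is the more relevant figure for attendance, where the plan expects little attrition. N = 128 is the cautious figure for substance use.

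**What to change.** Amend K.4 as follows.

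- For each Disability Beliefs Scale subscale, entered as a continuous score, add the belief-by-treatment-by-time term and its lower-order terms to each primary outcome model. If the factor analysis yields a different structure, apply this to the resulting subscales.
- Report the interaction estimate with its 95% CI, label it exploratory in keeping with the hypothesis, and state how many interactions were examined.
- Keep the covariate-only models for the separate question of what predicts outcome, and describe their results as prediction.
- Do not extend the interactions to every variable listed in K.4. Hypothesis 2 concerns beliefs about disability, and a wider set adds multiplicity.

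The cost is a short rewording and a few model terms, with no new data, visits or participants. The downsides are imprecise estimates and several interaction tests across the two primary outcomes. A wide interval should not be read as evidence that beliefs make no difference.
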